4.4 Safety Objectives

- To test the safety and feasibility of a 30-minute bicycle exercise in hyperglycemic patients
- To test the safety of an intensive lifestyle intervention within 3 months following study enrollment

5. STUDY OUTCOMES

5.1 Primary Outcome

The primary endpoint of this study is achievement of metabolic control with intensive lifestyle intervention 3 months after study enrollment. For the purpose of this study, metabolic control is defined as a fasting glucose < 7.6 mmol/l and an HbA1c below a target stratified for three groups according to HbA1c at baseline: HbA1c > 14 % → target < 10 %; HbA1c < 14 % and > 10 % → target < 8 %; HbA1c < 10 % → target < 7.5 %.

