Outcome(s):	
Primary: The primary endpoint of this study is achievement of metabolic control without anti-diabetic medication 3 months after study enrollment. For the purpose of this study, metabolic control is defined as an HbA1c below a target stratified for three groups according to HbA1c at baseline: HbA1c >14% → target < 10%; HbA1c < 14% and > 10% → target < 8%; HbA1c < 10% → target < 7.5%
 
Secondary:
 
 - Absolute HbA1c reduction per stratification group (groups consist of HbA1c > 14 %, HbA1c < 14 % and > 10 % and HbA1c < 10 %) - Change of HbA1c at 6 and 12 months after enrollment compared to control group - Proportion of patients achieving target per stratified group after 3 and 6 months without anti-diabetic medication other than Metformin - Changes in pH, base excess and bicarbonate 90 minutes after bicycle exercise compared to baseline - Change of weight at 3, 6 and 12 months after enrollment compared to baseline and to standard of care - Changes in blood glucose at the end of, as well as 30 and 90 minutes after bicycle exercise compared to baseline - Feasibility of bicycle exercise at study enrollment in the ER, defined as absence of problem reports through the study team (e.g. patient cooperation) - Safety of bicycle exercise, defined as: 
 o Absence of SAEs during the exercise o No signs of acute cardiopulmonary decompensation in patients during bicycle exercise o No necessity to prematurely terminate the bicycle intervention because of other health or safety concerns - Safety of intensive lifestyle intervention within 3 months following study enrollment, with the following endpoints: 
 o Number of SAEs in the intervention group compared to the control group o Number of rescue medication administered in the intervention group compared to the control group - Length of initial hospitalization, as well as number and length of re-hospitalizations and unplanned re-consultations within 3 months after initial consultation - Changes in physical activity at 6 months compared to baseline assessed by SIMPAQ questionnaire (Endpoint: hours of physical activity) - Changes in physical activity at 3 and 6 months compared to baseline assessed by actigraph (Endpoint: Stepgoal reached) - Number of anti-diabetic medication at 30, 60, 90 days, as well as 6 months and one year compared to baseline in both arms - Proportion of patients receiving insulin therapy after 6 months and one year in the intervention group compared to the control group - Absolute health-care related costs at 3, 6 and 12 months in both arms - Quality of life at 6 months in the intervention group compared to standard of care as assessed by SF-36 questionnaire.

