Study Product/Intervention:	
Patients will be randomized either to standard care or to a bicycle exercise followed by an intensive lifestyle intervention on top of non-pharmacological standard care.
 
After rehydration, patients allocated to the intensified lifestyle intervention group will be instructed to perform 30 minutes of bicycle exercise at 60 % of the calculated maximum heart rate (according to Franckowiak et al.)²⁰ followed by an intensive lifestyle intervention. Patients will be discharged if the clinical status is stable and no comorbidities require further hospitalization. Follow-up visits at the Clinic of Endocrinology for further instructions and consultation will be carried out after 2, 7, 30, 60 and 90 days, half a year and a year.
 
In order to monitor blood glucose levels, patients will be instructed on visit 2 to take measurements at home and will be asked to send their fasting glucose levels of the first week to the study team for monitoring of the metabolic situation. This will also be done in the week before visits of day 30 and 90.
 
The schedule for the intervention arm consists of 3 to 5 aerobic training sessions (duration 15-40 minutes each) and 2 resistance trainings per week, as well as weekly motivational coaching via telephone by the study psychologist. Everyday activity will be objectively monitored using the patient's mobile phone and a blinded actigraph (activity tracker). Exercise sessions will be monitored by weekly phone calls and documented. To assess baseline physical activity all patients will fill in the SIMPAQ questionnaire at baseline and at 6 months.

Control Intervention (if applicable):	
The control arm will consist of the standard care delivered by the involved centers.

Number of Participants with Rationale:	The aim of this study is to assess whether bicycle exercise followed by an intensive lifestyle intervention can sufficiently restore metabolic control without anti-diabetic drugs at 3 months after study enrollment as compared to a standard of care control group. Based on our clinical experience we expect that 80 % in the intervention group will reach the primary endpoint of metabolic control with no anti-diabetic drugs compared to only 40% in the usual care control group. The inclusion of 28 patients per group (n total 62 patients including 10 % lost to follow-up) will provide 80 % power at an alpha level of 0.05.

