SUSAR	Suspected unexpected serious adverse reaction
TMF	Trial master file

STUDY SCHEDULE

Study Periods	ER	Intervention Period								Follow-up	Telephone FU
Visit	1	2	3		4		5		6	7	8
Time (day)	0	2 +/- 1	7 +/- 3	weekly	30 +/- 7	weekly	60 +/- 14	weekly	90 +/- 14	180 +/- 14	1 year +/- 45
Patient information and informed consent	x										
Demographics	x										
Medical history	x										
Medication	x				x		x		x	x	x
ECG (electrocardiograph)	(x)										
In- /exclusion criteria	x										
Physical examination	x										
Vital signs	x	x	x		x		x		x	x	only weight
Fasting blood samples (including glucose, insulin and c-peptide)		x							x	x	
Glycated hemoglobin A1c	x						x		x	x	x
Randomization	x										
Bicycle intervention	x										
Diabetes counselling (i. e. general information, self glucose measurements)		x	(x)								
Nutrition counselling			x								
Telephone (coaching) interview				x		x		x			
Report about physical activity (SIMPAQ)		x								x	
Adverse events	x	x	x		x		x		x	x	
Actigraph readout			x						x	x	
Quality of life questionnaire SF-36		x								x	
Start of Metformin therapy									(x)		

Table 1 Study schedule of the intervention group. (x) optional

Study Periods	ER	standard care period	Follow-up	Telephone FU
Visit	1	6	7	8
Time (day)	0	90 +/- 14	180 +/- 14	1 year +/- 45
Patient information and informed consent	x			
Demographics	x			
Medical history	x			
Medication	x	x	x	x
ECG (electrocardiography)	(x)			
In- /exclusion criteria	x			
Physical examination	x			
Vital signs	x	x	x	only weight
Fasting blood samples (including glucose, insulin and c-peptide)	x	x	x	
Glycated hemoglobin A1c	x	x	x	x
Randomization	x			
Diabetes counselling (i. e. general information, self glucose measurements)	(x)	x		
Nutrition counselling	(x)	x		
Report about physical activity (SIMPAQ)	x		x	
Adverse events	x	x	x	
Quality of life questionnaire SF-36	x		x	
Start of Metformin therapy	(x)	(x)		

Table 2 Study schedule of the control group. (x) optional

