9.1.1 Assessment of Primary Outcome

Glycated hemoglobin A1c will be measured by the same means (POCT or venous blood sampling) as done at baseline, and 3 months after enrollment.

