11. STATISTICAL METHODS

Hypothesis

We hypothesize that lifestyle intervention lowers HbA1c effectively without antidiabetic drugs. The null-hypothesis (H_0) is that there will be no significant difference between the proportions of patients achieving metabolic control in the intervention group and the control group. The alternative hypothesis (H_1) is that there will be significantly more patients achieving metabolic control in the intervention group. For the purpose of this study, metabolic control is defined as a fasting glucose < 7.6 mmol/l and an HbA1c below a target stratified for three groups according to HbA1c at baseline: HbA1c $> 14\% \rightarrow$ target $< 10\%$; HbA1c $< 14\%$ and $> 10\% \rightarrow$ target $< 8\%$; HbA1c $< 10\% \rightarrow$ target $< 7.5\%$.

Determination of Sample Size

The aim of this study is to assess whether bicycle exercise followed by an intensive life style intervention can sufficiently restore metabolic control without anti-diabetic drugs as compared to a standard care control group.

Based on our clinical experience we assume that 80 % in the intervention group will reach the primary endpoint of metabolic control with no anti-diabetic drugs compared to only 40 % in the standard care control group.

A publication by Martinus et al.²¹ on adherence to a study sport program for newly diagnosed type 2 diabetes mellitus patients, shows up to 80 % adherence for the group that was additionally supported by a psychologist for increased motivation. The adherence to the program was significantly better in the group with support by the psychologist, as were the results regarding improvement of physiological parameters such as body mass, fat mass or strength.

A review on the effect of physical exercise on glycemic control found an average decrease of HbA1c by 0.6 mmol/l through exercise²² in diabetes patients at least one year after diagnosis and with a moderate hemoglobin elevation. Based on this data, our target ranges were extrapolated for patients with new-onset diabetes and higher HbA1c.

The inclusion of 28 patients per group (n total 62 patients including 10 % lost to follow-up) will provide 80 % power at an alpha level of 0.05. A number of 15 to 25 patients per center is envisaged.

Statistical Criteria of Termination of Trial

There will be no statistical criteria to terminate the trial early.

Planned Analyses

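### The primary endpoint is defined differently in the Synopsis, section 5.1 and section 11, and the 80%/40% rates behind the sample size belong only to the drug-free wording

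*Protocol*

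**What the plan says.** The protocol describes the primary endpoint in four places.

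- **Synopsis, Outcome(s).** The endpoint is "achievement of metabolic control without anti-diabetic medication 3 months after study enrollment", and "metabolic control is defined as an HbA1c below a target stratified for three groups according to HbA1c at baseline". There is no fasting-glucose criterion.
- **Section 5.1.** The endpoint is "achievement of metabolic control with intensive lifestyle intervention 3 months after study enrollment", and "metabolic control is defined as a fasting glucose < 7.6 mmol/l and an HbA1c below a target stratified for three groups". Nothing is said about anti-diabetic drugs.
- **Section 11.** The Hypothesis paragraph defines metabolic control in the same words as 5.1. Its opening sentence speaks of lowering HbA1c without drugs, but H0, H1 and the definition do not. The sample-size paragraph then assumes that 80% of the intervention group "will reach the primary endpoint of metabolic control with no anti-diabetic drugs compared to only 40 % in the standard care control group". The Synopsis rationale for the sample size ties the same rates to the same drug-free condition: "we expect that 80 % in the intervention group will reach the primary endpoint of metabolic control with no anti-diabetic drugs".
- **Section 9.1.1.** Only HbA1c is named as the primary-outcome measurement: "Glycated hemoglobin A1c will be measured by the same means (POCT or venous blood sampling) as done at baseline".

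The HbA1c targets by baseline level are the same wherever they appear. Sections 8.1.2 and 8.1.4 say that standard care usually includes oral anti-diabetic drugs or insulin. Section 8 (Dose/Device Modifications; Concomitant Interventions) allows standard-of-care or rescue drugs in the intervention arm as well.

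**The concern.** The texts disagree on two components of the endpoint: whether fasting glucose must be below 7.6 mmol/l, and whether a patient taking anti-diabetic drugs can count as a success. The phrase in 5.1 that ties success to the lifestyle intervention also cannot be applied to the control arm.

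Drug treatment is the usual care for controls, so the medication condition may decide the outcome for many of them. This is the one comparison the trial is sized for. The study is open-label (6.1.2) and the investigators do the analysis (11.1.2). With more than one definition in force, the primary result can depend on which page is followed, and nothing in the protocol prevents that choice from being made once outcomes are known.

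**Working it through.** **1. How each text classifies the same patient at month 3**

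| Patient | Synopsis | Section 5.1 | Section 11, sample-size wording |
|---|---|---|---|
| HbA1c and fasting glucose at target, on a drug | failure | success | failure |
| HbA1c at target, fasting glucose 8.0 mmol/l, drug-free | success | failure | failure |
| HbA1c and fasting glucose at target, drug-free | success | success | success |

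Section 5.1 is read here as silent on treatment, because its literal wording excludes every control.

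**2. The plan's own figure**

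Inputs from section 11: p1 = 0.80, p2 = 0.40, two-sided alpha 0.05, power 80%, 1:1 allocation.

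- Without continuity correction, n = [1.960·√(2·0.6·0.4) + 0.842·√(0.8·0.2 + 0.4·0.6)]² / 0.4² = (1.358 + 0.532)² / 0.16 = 22.3, so 23 per arm.
- With continuity correction, n = (22.3/4)·[1 + √(1 + 4/(22.3·0.4))]² = 27.1, so **28 per arm**, as stated.
- Loss to follow-up: 56 × 1.10 = 61.6, so 62, as stated.
- Exact power of the planned Fisher test, summing the binomial probabilities of all 29 × 29 outcomes at 28 per arm with two-sided p < 0.05: **82.3%**.

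The arithmetic is sound for 80% versus 40%. The open question is which endpoint those two rates describe.

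**3. Power if drug-treated patients may count as successes**

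Same enumeration, 28 per arm. Every rate in this table is an assumption, except that 80% is the planned intervention rate.

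| Control rate | Intervention 80% | Intervention 85% | Intervention 90% |
|---|---|---|---|
| 50% | 57.5% | 75.2% | 89.1% |
| 60% | 28.2% | 45.4% | 65.9% |
| 70% | 8.1% | 17.1% | 33.2% |

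The 85% and 90% columns allow for rescue-treated intervention patients who also become successes. With the intervention arm at 80%, the continuity-corrected size for 80% power is 45, 91 and 313 per arm for control rates of 50%, 60% and 70%.

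In the other direction, a strict drug-free rule could put the control rate below 40%. At 80% versus 30% the power is 95.6%, and at 80% versus 20% it is 99.6%.

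**4. How few patients it takes**

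80% and 40% of 28 are 22.4 and 11.2, taken as 22 and 11.

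| Intervention | Control | Fisher p |
|---|---|---|
| 22/28 | 11/28 | 0.006 |
| 22/28 | 14/28 | 0.0496 |
| 22/28 | 15/28 | 0.089 |
| 23/28 | 15/28 | 0.044 |
| 23/28 | 16/28 | 0.080 |

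Reclassifying three controls leaves the result just significant, and a fourth removes significance. One intervention patient reclassified as well restores it, and one further control removes it again.

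**5. The glucose criterion**

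The protocol gives no rate for it, and section 11 may already include it in 80%/40%. Its effect is not quantified.

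**The case against.** The strongest reply is that the intended endpoint is plainly drug-free. The Synopsis says so twice, section 11 says so in its opening hypothesis and its sample-size paragraph, and 5.1 is merely silent. The secondary outcome that tolerates metformin but no other drug reads like a relaxation of a drug-free primary. On that view the power loss belongs to the least supported reading. This has weight, but it does not settle the matter. Section 5.1 is where the endpoint is formally defined, and the metformin outcome shows that the protocol writes a drug rule when it wants one. The reply also leaves the glucose contradiction untouched.

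Several narrower points stand:

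- Section 11 is a distinct version only through its hypothesis and sample-size wording. Its definition sentence is that of 5.1.
- Section 9.1.1 fixes how HbA1c is measured. It is incomplete if glucose counts, but it does not define the endpoint.
- How to classify a patient whose rescue drug was stopped before visit 6 could be left to an analysis plan.
- Section 8.1.1 allows metformin in the intervention arm only after 3 months, while Concomitant Interventions exempts it without a time limit. Those passages also need reconciling.
- The counts in step 4 are illustrative. In any trial this small, a few reclassified patients can move p across 0.05.
- An analysis plan that is not shown here may fix one definition, but it would then contradict at least one page of the protocol.

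**Conclusion.** The concern holds, and the text must be corrected. The Synopsis contradicts 5.1 and section 11 on fasting glucose. Section 5.1 lacks the drug-free condition on which the Synopsis and the sample-size paragraph rely. Both differences change who counts as a success.

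The sample size itself is correctly calculated for 80% versus 40%. The stated 80% power is supported only if drug-treated patients count as not achieved. If they may succeed, power at 28 per arm ranges from 8% to 89% over the assumed rates (control 50–70%, intervention 80–90%). The contradiction does not depend on these assumptions; only its size does.

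**What to change.** Use one definition, applied identically to both arms, in the Synopsis and sections 5.1, 9.1.1 and 11. It should state:

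1. whether fasting glucose below 7.6 mmol/l is required and, if so, list it in 9.1.1 beside HbA1c;
2. whether anti-diabetic drug use, including rescue, counts as not achieved, and whether this is judged at visit 6 or over the whole period since enrollment.

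Replace the phrase in 5.1 that ties success to the lifestyle intervention with wording that fits controls too. Restate or re-justify 80%/40% and the power for the chosen definition. Which rule to adopt is the authors' choice.

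First enrollment was planned for 11/2018 and this version is dated 30.10.2023. The choice should therefore be made and dated before anyone compares outcomes by arm, and the restated rates should not come from the trial's own results by arm.

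The cost is protocol wording and a rewritten power paragraph. No new data are needed: Tables 1 and 2 already schedule fasting glucose, HbA1c and medication at visit 6 in both arms. The downside is that the sample size may have to rise if drug-treated patients can count as successes.

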5.2 Secondary Outcomes

Secondary outcomes are as follows:

- Absolute HbA1c reduction per stratification group (groups consist of HbA1c > 14 %, HbA1c < 14 % and > 10 % and HbA1c < 10 %)
- Change of HbA1c at 6 and 12 months after enrollment compared to control group
- Proportion of patients achieving target per stratified group after 3 and 6 months without anti-diabetic medication other than Metformin
- Changes in pH, base excess and bicarbonate 90 minutes after bicycle exercise compared to baseline
- Change of weight at 3, 6 and 12 months after enrollment compared to baseline and to standard of care
- Changes in blood glucose at the end of, as well as 30 and 90 minutes after bicycle exercise compared to baseline
- Feasibility of bicycle exercise at study enrollment in the ER, defined as absence of problem reports through the study team (e.g. patient cooperation)
- Safety of bicycle exercise, defined as:
 - o Absence of SAEs during the exercise
 - o No signs of acute cardiopulmonary decompensation in the patient during bicycle exercise
 - o No necessity to prematurely terminate the bicycle intervention because of other health or safety concerns
- Safety of intensive lifestyle intervention within 3 months following study enrollment, with the following endpoints:
 - o Number of SAEs in the intervention group compared to the control group
 - o Number of rescue medication administered in the intervention group compared to the control group
- Length of initial hospitalization, as well as number and length of re-hospitalizations and unplanned re-consultations within 3 months after initial consultation
- Changes in physical activity at 6 months compared to baseline assessed by SIMPAQ questionnaire (Endpoint: hours of physical activity)
- Changes in physical activity at 3 and 6 months compared to baseline assessed by actigraph (Endpoint: Stepgoal reached)
- Number of anti-diabetic medication at 30, 60, 90 days, as well as 6 months and one year compared to baseline in both arms
- Proportion of patients receiving insulin therapy after 6 months and one year in the intervention group compared to the control group
- Absolute health-care related costs at 3, 6 and 12 months in both arms
- Quality of life at 6 months in the intervention group compared to standard of care as assessed by SF-36 questionnaire.

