Background and Rationale:	
Lifestyle intervention is a fundamental aspect in the treatment of type 2 diabetes. Implementation of lifestyle changes early after diagnosis often suffices to control metabolic dysregulation and may even have a durable impact. However, implementation of these changes is often difficult for multiple reasons including noncompliance as well as doubt on efficacy of sport and diet changes compared to drugs. Furthermore, most patients with type 2 diabetes remain asymptomatic for a prolonged period of time. Thus, they lack an immediate relief of symptoms and do not feel the benefit of changes in lifestyle. Often, untreated type 2 diabetes first manifests itself with symptoms of polyuria and polydipsia. This offers a unique opportunity to demonstrate the potential of lifestyle changes. However, in daily practice, symptomatic patients with polyuria and polydipsia or with HbA1c levels >10% at diagnosis are typically referred to an emergency room, hospitalized and treated with drugs as a first line treatment.
 
In the present study, we aim to implement a lifestyle intervention as a first-line treatment in recent onset type 2 diabetes. In the emergency room, the bed will symbolically be removed and the patient requested to perform a bicycle exercise. Non-ER patients will be invited to perform the bicycle exercise as soon as possible. We expect from this educational trigger that patients will realize the therapeutic power of sport. Preliminary interventions using this approach at our emergency room demonstrated the potential of such an intervention. However, internal and external validation, efficacy and safety of a lifestyle intervention in an emergency room remain to be shown in a multi-center controlled study.

Objective(s):	The aim of the study is to test the efficacy, feasibility, and safety of a bicycle exercise followed by an intensive lifestyle intervention for 3 months in patients with recent onset and medically untreated type 2 diabetes.

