7. STUDY POPULATION

Eligibility Criteria

Participants fulfilling all of the following inclusion criteria are eligible for the study

- Able to give informed consent as documented by signature (Appendix ICF)
- Type 2 diabetes diagnosed within the last two years according to the ADA-criteria
- Age \geq 18 years
- HbA1c \geq 7.5 %

The presence of any one of the following exclusion criteria will lead to exclusion of the participant:

- Clinically unstable patient as defined by the physicians on duty e. g. signs of new ischemia in the ECG, systolic blood pressure \geq 200 mmHg, fever \geq 38.5 °C, symptoms of SIRS or reduced vigilance.
- Anti-diabetic medication for \geq 24 hours
- Inability to perform a bicycle exercise during 30 minutes
- Previous lifestyle intervention by an endocrinologist
- Engagement in physical activity more than five times per week
- Enrollment in other interventional study

Recruitment and Screening

Patients are recruited after seeking medical consultation at the emergency room, medical outpatient clinic of the respective study centers or their general practitioners. Patients will be assessed and enrolled in the study by the study team.

Assignment to Study Groups

Patients are randomized to the intervention or the control arm using a computer-generated number after agreeing to participate in the study.

Criteria for Withdrawal/Discontinuation of Participants

Participants may withdraw or be withdrawn at any time. Subjects who discontinue participation may be replaced. Reasons for discontinuation are:

- Participant withdraws informed consent
- Participant does not comply with study treatment or the concomitant procedures. Non-compliance for this study is defined as completion of less than 50% of the training program during two weeks
- Pregnancy
- Participant is no longer willing to continue the study because of any reason
- The incidence or severity of adverse events (AEs) indicate a potential health hazard to the participant

Withdrawal will be documented in the database with all other study data.

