8.1.4 Control Intervention

The control arm for this study will receive standard type 2 diabetes treatment after study enrollment. This treatment usually consists of a limited lifestyle intervention and oral anti-diabetic medication (i.e. Metformin, SGLT2-inhibitors, DPP-Inhibitors, GLP-1-receptor agonists etc.) or insulin therapy.

Dose/Device Modifications

Therapy for the participants of the intervention group has to be reassessed if:

- glucose values remain elevated above 15 mmol/l for more than 7 consecutive days
- in case of symptomatic hyperglycemia or re-hospitalization

In these cases, standard of care according to national and international guidelines will be implemented.

Compliance with Study Intervention

Patients in the intervention arm will be motivated by a specially trained psychologist and provided with an actigraph to monitor daily step count, overall physical activity and the scheduled training sessions. Personal motivation for the training sessions will be supported through telephone interviews, during study visits and with continuous self-evaluation. If the bicycle exercise is not completed or completed partly, this will be documented in the CRF.

Data Collection and Follow-up for Withdrawn Participants

Participants may withdraw or be withdrawn at any time. Subjects who discontinue participation will not be replaced. Withdrawal will be documented in the database with all other study data. All gathered data and samples until withdrawal of informed consent will be used anonymously for analysis. Follow-up will not take place if the patient has withdrawn informed consent, in all other cases follow-up will take place as planned.

Trial-specific Preventive Measures

Participants of the bicycle and intensive lifestyle modification group will, in addition to the general clinical visits, be closely monitored and coached with weekly telephone calls, thereby ensuring appropriate glucose management. If needed, standard of care medical treatment will be initiated also in the interventional group. All patient specific data will be recorded in an electronic case report form (eCRF).

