11.1.3 Secondary Analyses

We will use the Wilcoxon Rank Sum test for not normally distributed data and Fisher's exact test for categorical data to compare changes between the two groups. All tests will be two tailed; $p < 0.05$ will be defined as significant. Data will be analyzed using STATA, Graph Pad Prism and IBM SPSS.

The parameters assessed via blood sampling during and after the bicycle exercise will be analyzed using descriptive statistics and appropriate graphical representation.

Values of pH, base excess and bicarbonate at 120 minutes after beginning of the bicycle exercise will be compared to the baseline values using medians and interquartile range as well as appropriate graphical representation. The statistical significance of the difference between the two medians will be tested using the Wilcoxon signed-rank test for paired data.

The same statistical procedure will be applied to the values of blood glucose at the end of, as well as 60 and 120 minutes after beginning of the bicycle intervention.

Safety outcomes (please refer to chapter 5.2) will be illustrated using descriptive statistics.

Re-hospitalization and unplanned re-consultation rate 3 months after study enrollment will be quantified by number of hospitalizations and/or physician re-consultations as well as total length of hospitalization(s) in days. Data will be tested using the Mann-Whitney U-test.

SIMPAQ questionnaire results will be depicted using descriptive statistics and medians of the two groups evaluated using the Mann-Whitney U-test.

Results of the actigraph readouts at baseline, 3 months and 6 months will be compared inter-individually to assess if the endpoint has been fulfilled or not.

Number of anti-diabetic medication at 1, 2, 3 and 6 months as well as one year compared to baseline will be depicted using Graph Pad Prism. Average number of medication in both groups will be compared at 3 and 6 months after baseline.

Health-care related costs will be calculated for each study arm based on actual costs in respective cantons for medication as well as according to Tarmed (outpatient-clinic tariff system).

SF-36 questionnaire will be evaluated using IBM SPSS and compared between the two groups using the Mann-Whitney U-test at baseline and after 6 months.

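### Feasibility of the bicycle ride is defined only by the absence of problem reports in the ER, so incomplete rides need not count and rides outside the ER are left out

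*Protocol*

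**What the plan says.** Protocol 4.1 and the synopsis name feasibility beside efficacy and safety as what the study tests. Objective 4.4 is "To test the safety and feasibility of a 30-minute bicycle exercise in hyperglycemic patients", with no restriction on where the ride takes place.

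The only outcome that serves this aim is in 5.2, with the same wording in the synopsis: "Feasibility of bicycle exercise at study enrollment in the ER, defined as absence of problem reports through the study team (e.g. patient cooperation"). It states no completion criterion and does not define what must be reported as a problem.

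Three other places bear on it:

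- Section 8, under Compliance with Study Intervention: "If the bicycle exercise is not completed or completed partly, this will be documented in the CRF".
- Section 7, in the part on recruitment: "Patients are recruited after seeking medical consultation at the emergency room, medical outpatient clinic of the respective study centers or their general practitioners". The synopsis background adds: "Non-ER patients will be invited to perform the bicycle exercise as soon as possible".
- The safety outcome that follows in 5.2 includes "No necessity to prematurely terminate the bicycle intervention because of other health or safety concerns".

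For analysis, 11.1.3 says: "Safety outcomes (please refer to chapter 5.2) will be illustrated using descriptive statistics". It names neither feasibility nor completion of the ride.

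**The concern.** Whether the ride is feasible is first a question of delivery: did the patients allocated to it start it and finish it? The outcome asks something else, namely whether the study team filed a problem. The two agree only if every ride that failed led to a report, and the protocol does not require that. A ride left undone for lack of time, for logistics or by preference can pass without a report and without touching the safety outcome.

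The ER limit is a second gap. A patient recruited through an outpatient clinic or a general practitioner may ride outside the ER. That ride belongs to the objective in 4.4 but not to the outcome in 5.2.

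At stake is what the trial can say about one of its stated aims. A favourable feasibility result could not be read as evidence that the ride was delivered to those allocated to it, although the data to show this are being collected.

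**Working it through.** The protocol states no feasibility rate, denominator or threshold, so there is no figure to reproduce. The check is mainly textual.

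**Which events the outcome captures**

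| Event in the intervention arm | Counts against feasibility as defined? | Counts elsewhere in 5.2? | Recorded in the CRF? |
|---|---|---|---|
| Ride in the ER, problem report filed (e.g. cooperation) | Yes | Not necessarily | Yes, if incomplete |
| Ride in the ER stopped for health or safety reasons | Only if also filed as a problem | Yes, under safety | Yes |
| Ride in the ER not started or cut short for another reason, no report filed | No | No | Yes |
| Ride outside the ER not started or cut short | No, outside the wording | Only if a safety reason | Yes |
| Ride outside the ER completed | Not counted either way | Safety only | No incompleteness to record |

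The third and fourth rows carry the point. The third depends on an undefined report, and the fourth follows directly from the words that tie the outcome to the ER. The CRF record would identify both.

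**Illustration of size**

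- Arm size: "The inclusion of 28 patients per group (n total 62 patients including 10 % lost to follow-up"), with 1:1 allocation (6.1.1), gives 62 / 2 = 31 in the intervention arm.
- Number of incomplete rides without a report: not in the documents, so assumed.
- Number enrolled in the ER: not in the documents, so assumed.

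Completion = (31 − k) / 31, where k is the number of incomplete rides without a report. The exact (Clopper-Pearson) 95% intervals are:

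- k = 0: 31/31 = 100% (89-100%)
- k = 3: 28/31 = 90% (74-98%)
- k = 5: 26/31 = 84% (66-95%)

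If all 31 were enrolled in the ER and no problem were reported, the outcome as defined would read 100% in each of these three cases.

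Coverage of the arm = (number enrolled in the ER) / 31:

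- 25/31 = 80.6%
- 20/31 = 64.5%
- 15/31 = 48.4%
- 10/31 = 32.3%

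A perfect result in the ER patients alone has the lower 95% limit 0.025^(1/n). This is 83% for n = 20 and 69% for n = 10, against 89% for n = 31.

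The sample size is set by the primary endpoint and does not depend on any of this.

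**The case against.** The strongest reply is that failed rides would be reported anyway. Patient cooperation is the protocol's own example of a problem, a patient who refuses or stops is the obvious case of it, and a member of the study team is present throughout the ride (9.1.3.4). Stops for health or safety reasons enter the neighbouring safety outcome, which has no ER limit. This stands in part. A reader might infer from 5.2 that a ride not started or not finished never enters the result. The documents do not support that, because it can enter through a report. What they leave open is whether it must.

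A second reply is that an ER-specific measure suits the trial's interest in the emergency setting (synopsis background; section 3, Risks/Benefits). That is fair, and it is a reason to report the ER patients separately. It does not explain why the objectives carry no ER limit.

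A reader might also infer that patients recruited outside the ER are the most likely to ride late or not at all. Nothing in the protocol shows this. Section 9.1.5 places the ride at Visit 1, Day 0, for the whole intervention arm.

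A third reply is that tabulating a descriptive secondary outcome belongs in a statistical analysis plan. Tabulation does, but here the protocol itself fixes the definition of the outcome.

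Finally, the ability to ride for 30 minutes is already required, since inability is an exclusion criterion. That is judged before the ride and does not show that the ride took place.

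**Conclusion.** The point holds in a limited form. As worded, the feasibility outcome does not require an incomplete ride to count as a failure, and it excludes rides outside the ER. The protocol already collects the more direct measure and does not use it. The primary endpoint and the sample size are unaffected, but the trial's answer to one of its named aims is weakened, so the definition should be changed.

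No size can be given from the documents. The gap between 100% and 90% (95% CI 74-98%) rests on three assumptions: 31 patients allocated, all enrolled in the ER, and exactly 3 incomplete rides that nobody filed as a problem. It shows what the definition permits. It is not a forecast that the trial will overstate feasibility.

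**What to change.** In 5.2 and in the synopsis, define feasibility as the proportion of all patients randomised to the intervention, in any setting, who started and completed the 30-minute ride according to the CRF record. Count never-started and partial rides as not feasible. Report the proportion with a 95% CI, overall and separately for ER and non-ER patients. List the problem reports descriptively, as reasons.

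Do not make the planned intensity part of the criterion. For the ride itself, 9.1.3.4 specifies only blood pressure at intervals, and no recording of attained intensity is specified.

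The completion record already exists, so this part needs no new data. The protocol does not say how the recruitment setting is captured, and this should be confirmed before reporting by setting is promised. The change amends the outcome wording and may need ethics committee approval if it is classed as substantial. The trial is open-label and enrolment was planned to start in 11/2018, so the amendment should be dated and made before the feasibility data are tabulated. The downside is that the stated feasibility may be less favourable.
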